2.8.1. Demography

Demographic information relating to the participant's sex, age, and race will be recorded at Screening in the eCRF.

Medical history of each participant will be collected and recorded in the eCRF. Significant findings that were present prior to the signature of the informed consent will also be included in the eCRF.

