3.6. Assignment to Study Intervention (Part B)

Randomization will be performed using an IRT. Approximately 3000 participants will be randomly assigned to treatment in this study in a 1:1 ratio to 1 of 2 treatment groups to receive either a single dose of mRNA-1010 or a single dose of a licensed SD seasonal influenza vaccine (Fluarix Quadrivalent, Table 10). Randomization will be stratified by previous flu season (since September 2022) vaccination status (received or not received; if received, was it from prior participation in the mRNA-1010-P302 study [yes/no]).

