2.5.3.1. Analysis of Primary Endpoints

 GMT as measured by HAI against 4 vaccine-matched influenza virus A and B strains at Day 29

The GMT will be calculated using the following formula:

$$GMT = 2^{\left\{\frac{\sum_{i=1}^{n} \log_2(t_i)}{n}\right\}}$$

where, for n participants, t_i is the immunogenicity titer measurement for participant i.

An ANCOVA model will be carried out. The model will include the log-transformed HAI titers at Day 29 as the dependent variable, treatment group as the fixed variable, log-transformed baseline HAI titers as a fixed covariate, adjusting for the stratification factors. The GLSM and its corresponding 95% CI results in log-transformed scale estimated from the model will be back-transformed to obtain these estimates in the original scale, as an estimate of the GMT.

The GMR for mRNA-1010 vs. active comparator, estimated by the ratio of GLSM and the corresponding 2-sided 95% CI will be provided to assess the treatment difference and calculated by back-transforming of the difference estimated from the ANCOVA model. The corresponding 2-sided 95% CI of GMR will be provided to assess the difference in immune response between the mRNA-1010 group compared to the active comparator group at Day 29. For each strain, the noninferiority of GMT will be considered demonstrated if the lower bound of the 95% CI of the GMR is >0.667 based on a noninferiority margin of 1.5.

Descriptive statistics (n, median, min, max) will also be provided for the GMT of HAI titers with corresponding 95% CI at each timepoint. The 95% CIs will be calculated based on the t-distribution of the log-transformed values then back transformed to the original scale for presentation. In addition, the GMT with corresponding 95% CI will be plotted at each time point respectively.

• Proportion of participants reaching seroconversion at Day 29 as measured by HAI

The number and percentage of participants with seroconversion at Day 29 will be provided with 2-sided 95% CI using the Clopper-Pearson method. To compare the seroconversion rates between the treatment groups, the Miettinen-Nurminen's method will be used to calculate the 95% CI for the difference in seroconversion rates at Day 29. For each strain, the noninferiority of seroconversion rate will be considered demonstrated if the lower bound of the 95% CI of the seroconversion rate difference is > -10% based on a noninferiority margin of 10%.

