3.5.3.3. Subgroup Analysis

To assess the consistency of immunogenicity response of mRNA-1010 across subgroups, subgroup analysis of the co-primary endpoints may be conducted by subgroups defined by age group, previous flu vaccine status, race, sex, and BMI category (see Table 8), based on the PP Immunogenicity Set. For each subgroup category, the co-primary immunogenicity endpoints will be analyzed using the same statistical methods as for primary analysis. Additional details are documented in Section 2.5.3.1.

If the number of participants in a subgroup is less than 10% of sample size in the analysis set, it may be combined with other subgroups for the subgroup analyses.

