4.3.4. Randomization

Randomization will be performed using an IRT. Approximately 3000 participants will be randomly assigned to treatment in this study in a 1:1 ratio to 1 of 2 treatment groups to receive either a single dose of mRNA-1010 or a single dose of a licensed HD seasonal influenza vaccine (Fluzone HD Quadrivalent, Table 9). Randomization will be stratified by the previous flu season (since September 2022) vaccination status (Received, Received from mRNA-1010-P302.; Not received).

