Target Population	Adults aged at least 18 years inclusive who receive the assigned IP administration, complied with immunogenicity blood sampling to have a baseline and Day 29 antibody assessment as measured by HAI assay after the IP administration, and have no significant protocol deviations impacting the key or critical data. Participants with RT-PCR- confirmed influenza between Days 1 to 29 will be removed from the PP Immunogenicity Set	Adults aged at least 18 years inclusive who receive any IP administration and complied with immunogenicity blood sampling to have a baseline and Day 29 antibody assessment as measured by HAI assay.	
Endpoint	GMT of anti-HA levels on Day 29	As per Estimand 1a.	
Treatment Conditions	mRNA-1010 vs. active comparator (Fluarix Quadrivalent)	As per Estimand 1a.	

Population-Level Summary Intercurrent Event Strategy	Immune response to seasonal influenza defined as GMT of anti- HA level as measured by HAI assay using an ANCOVA model on the log-transformed tiers on Day 29, with the vaccination group as the fixed variable, adjusted for stratified age group used for randomization and log-transformed baseline tiers.	As per Estimand 1a.
IcEv1 (early discontinuation or unrelated death)	Principal stratum	Principal stratum
IcEv2 (alternative influenza vaccine)	Principal stratum	Treatment policy
IcEv3 (COVID-19 vaccine)	Principal stratum	Treatment policy
IcEv4 (prohibited medications)	Principal stratum	Treatment policy
IcEv5 (early infection)	Principal stratum	Treatment policy
IcEv6 (wrong vaccination)	Principal stratum	Treatment policy

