Estimand Description	Immune response to influenza measured as GMT of vaccine- matched anti-HA level as measured by HAI assay on Day 29 in adults aged at least 18 years inclusive and less than 65 years who receive IP administration and complied with immunogenicity blood sampling to have a baseline and Day 29 antibody assessment without significant protocol deviations impacting immune response.	Immune response to seasonal influenza measured as GMT of vaccine-matched anti-HA level as measured by HAI assay on Day 29 in adults aged at least 18 years or inclusive and less than 65 years who receive IP administration irrespective of any significant protocol deviations impacting immune response and complied with immunogenicity blood sampling to have a baseline and Day 29 antibody assessment as measured by HAI assay.
Target Population	Adults aged at least 18 years inclusive and less than 65 years who receive the assigned IP administration, complied with immunogenicity blood sampling to have a baseline and Day 29 antibody assessment as measured by HAI assay after the IP administration, and have no significant protocol deviations impacting the key or critical data.	Adults aged at least 18 years inclusive and less than 65 years who receive any IP administration and complied with immunogenicity blood sampling to have a baseline and Day 29 antibody assessment as measured by HAI assay.
Endpoint	GMT of anti-HA levels on Day 29	As per Estimand 1a.
Treatment Conditions	mRNA-1010 vs. active comparator (Fluarix Quadrivalent)	As per Estimand 1a.
Population-Level Summary	Immune response to seasonal influenza defined as GMT of anti- HA level as measured by HAI assay using an ANCOVA model on the log-transformed tiers on Day 29, with the vaccination group as the fixed variable, adjusted for stratified previous flu vaccination status used for randomization and log-transformed baseline tiers.	As per Estimand 1a.
Intercurrent Event Strategy		

IcEv1 (early discontinuation or unrelated death)	Principal stratum	Principal stratum	
IcEv2 (alternative influenza vaccine)	Principal stratum	Treatment policy	
IcEv3 (COVID-19 vaccine)	Principal stratum	Treatment policy	
IcEv4 (prohibited medications)	Principal stratum	Treatment policy	
IcEv5 (early infection)	Principal stratum	Treatment policy	
IcEv6 (wrong vaccination)	Principal stratum	Treatment policy	

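### In Parts B and C the GMT ANCOVA leaves out age, a recorded baseline variable; the analysis is valid, but a little precision for the secondary superiority tests may go unused.

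*SAP*

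**What the plan says.** **Randomisation.** Part B: "Randomization will be stratified by previous flu season (since September 2022) vaccination status" (Protocol 3.6; SAP 3.3.4 agrees). Part C: "Randomization will be stratified by the previous flu season (since September 2022) vaccination status" (SAP 4.3.4; Protocol 4.6 agrees). Age is not a stratum in either Part.

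**Model.** The ANCOVA in SAP 2.5.3.1 has treatment group and "log-transformed baseline HAI titers as a fixed covariate, adjusting for the stratification factors". SAP 3.5.3.1 and 4.5.3.1 refer Parts B and C back to it, and SAP 3.5.3.4 uses the same model for superiority. Tables 18 and 19 spell out the result: "adjusted for stratified previous flu vaccination status used for randomization and log-transformed baseline tiers".

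**Part A.** Age group (18 to <50, 50 to <65, 65 and over) is a randomisation stratum in SAP 2.3.4, and Table 17 has the model "adjusted for stratified age group used for randomization and log-transformed baseline tiers".

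**Availability of age.** "Demographic information relating to the participant's sex, age, and race will be recorded at Screening in the eCRF" (Protocol 2.8.1, applied to Parts B and C by reference). SAP Table 8 splits Part B at 50 and Table 11 splits Part C at 75, for subgroup use only: "subgroup analysis of the co-primary endpoints may be conducted by subgroups defined by age group, previous flu vaccine status" (SAP 3.5.3.3; SAP 4.5.3.3 is similar for Part C).

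**The concern.** The covariate list is tied to the strata, so age left the model when it left the randomisation, and neither document gives a reason. If Day 29 titre varies with age after allowing for baseline titre and prior vaccination, that variation stays in the residual error and widens the interval for the geometric mean ratio (GMR). An optional subgroup analysis by age adds no precision to the overall ratio.

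Any effect would matter mainly for GMT superiority, planned at about 79.5% power per strain. Under SAP 3.5.3.4 the A-strain GMT result governs whether A-strain seroconversion is tested. The A-strain results then set whether the B strains are tested at two-sided 0.025 or 0.0125.

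**Working it through.** **Inputs (SAP 3.3.3 and 4.3.3).** 3000 randomised and 15% excluded give 2550, or 1275 per arm. The SD of natural-log titre is 1.5. GMT noninferiority uses margin 1.5 at one-sided 0.025. The assumed GMR is 0.90 in the SAP for both Parts; Protocol 3.9.3 has 0.95 for Part B. Superiority uses GMR 1.2 at two-sided 0.025.

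**Input not in the documents.** R², the share of residual log-titre variance that age explains after baseline titre and vaccination status. It is assumed to lie between 0% and 5%.

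**1. Reproduce the plan.**
- SE of the log GMR = 1.5 × √(2/1275) = 0.0594.
- Noninferiority, one strain, GMR 0.90: Φ[(ln 0.90 + ln 1.5)/0.0594 − 1.960] = 0.9990. Four strains, taken as independent: 0.9990⁴ = 99.6%. At GMR 0.95 the result is 99.99%. The plan says at least 99%.
- Superiority, one strain: Φ[ln 1.2/0.0594 − 2.2414] = Φ(3.069 − 2.2414) = 79.6%. The plan says about 79.5%.
- The same test at two-sided 0.0125 (critical value 2.4977): 71.6%.

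**2. Add age.** The residual SD becomes 1.5 × √(1 − R²).

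| Assumed R² | CI width | NI, 4 strains, GMR 0.90 | Superiority, 0.025 | Superiority, 0.0125 |
|---|---|---|---|---|
| 0% | unchanged | 99.60% | 79.6% | 71.6% |
| 1% | −0.5% | 99.64% | 80.0% | 72.1% |
| 2% | −1.0% | 99.67% | 80.5% | 72.7% |
| 5% | −2.5% | 99.75% | 81.8% | 74.2% |

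**3. What those R² values imply.** With an assumed even split between two age groups and a GMT gap of d on the log scale, R² = (d/2)²/1.5². A 1.25-fold gap gives about 0.6% and a 1.5-fold gap about 1.8%. Reaching 1% needs about 1.35-fold, and 5% needs about 1.96-fold.

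**4. If 1.5 is the SD before baseline adjustment.** The SAP describes it only as the SD of the log-transformed levels. Suppose baseline titre explains an assumed 20% to 40% of the variance. Superiority power at 0.025 is then already 88.3% to 95.7%. Age at an R² of 1% to 5% adds 0.3 to 1.7 points at the lower end of that baseline range and 0.2 to 0.9 at the upper end.

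**5. Seroconversion.** Four-strain noninferiority power, by the normal approximation under independence, is 98.2% in Part B (58% v 59%, 48% v 49%) and 93.3% in Part C (58% v 60%, 48% v 50%). The plan says at least 98% and at least 93%. Seroconversion therefore limits the overall power. It uses an unadjusted Miettinen-Nurminen interval, which an ANCOVA covariate does not touch.

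**The case against.** The strongest reply is that nothing is wrong. Protocol and SAP agree on strata and covariates, and leaving a prognostic covariate out of a randomised comparison is valid. That stands.

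The Part A contrast is also weaker than it looks. Part A enrols all adults, while Parts B and C are already divided at 65. Part A's age strata would have one level in Part C, and only the cut at 50 would survive in Part B. The contrast shows that the sponsor has modelled age before, not that Parts B and C contradict Part A.

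The size rests on an assumption, and within these restricted age ranges an R² near zero is as compatible with the documents as 5%. That stands too, which is why the range starts at zero.

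A reader might infer two further harms:
- **Chance age imbalance distorts the GMR.** This is not a separate harm. Such imbalance is part of the residual variance that the interval already reflects, and age is summarised by arm (SAP 3.5.2.2 and 4.5.2.2), so an imbalance would be visible.
- **Not stratifying by age costs precision.** It does not, by itself, in a model without age; and age can be adjusted for without being a stratum.

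The reply leaves one thing unanswered: the covariate is already collected and uses about one degree of freedom out of roughly 2,500.

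**Conclusion.** The point holds as an optional refinement of a valid analysis. For an assumed R² of 0% to 5%, GMT superiority power per strain rises by 0 to 2.2 points at two-sided 0.025 (81.8 − 79.6) and by 0 to 2.6 points at 0.0125 (74.2 − 71.6). This takes 1.5 as the residual SD and a true GMR of 1.2. If 1.5 is the unadjusted SD, planned power at 0.025 is already higher and the gain from age is generally smaller.

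It would be tempting to conclude that the omission weakens the primary objective or explains the 79.5% superiority power. The documents support neither. Four-strain GMT noninferiority moves only from 99.60% to 99.75% at the top of the assumed range, and 79.5% follows from the planned sample size, SD, GMR and alpha. Low priority.

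**What to change.** Before unblinding of the Part concerned, add age at screening as a fixed covariate in SAP 2.5.3.1 as applied to Parts B and C, and in Tables 18 and 19. Use the same model for noninferiority and superiority. Age may be continuous or in the SAP's own categories (18 to <50 and 50 to <65 in Part B; 65 to <75 and 75 and over in Part C); fix the choice in advance. Leave randomisation unchanged.

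The change needs no new data and no new procedure. It may need more than a SAP edit. Protocol 2.9, which Sections 3.9 and 4.9 apply to Parts B and C, calls for a protocol amendment when methods for primary or key secondary hypotheses change before unblinding, and the ANCOVA is specified in Protocol 2.9.5.1. The SAP introduction says that the SAP prevails where methods differ, so the sponsor should decide which rule governs and align the two texts.

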7.9. Definition of TEAE of Special Interest by SMQ

The following applies to Part A, Part B, and Part C:

Table 20 List of TEA	E of Special	Interest by	SMQ
----------------------	--------------	-------------	-----

TEAE of Special	Type of	Broad or Narrow	SMQ Search
Interest*	MedDRA Query	Search **	Criteria
Anaphylactic Reaction	SMQ	Algorithm	A or (B and C) or (D
			and (B or C)), Specified
			PT and algorithm
			approach included in
Angioedema	SMQ	Narrow	Specified PT terms
Arthritis	SMQ	Narrow	Specified PT terms
Cardiac Arrhythmias	SMQ	Narrow	Specified PT terms
Cardiac Failure	SMQ	Narrow	Specified PT terms
Cardiomyopathy	SMQ	Narrow	Specified PT terms
Central Nervous System	SMQ	Narrow	Specified PT terms
Vascular Disorders			
Convulsions	SMQ	Narrow	Specified PT terms
Demyelination	SMQ	Narrow	Specified PT terms
Embolic and Thrombotic	SMQ	Narrow	Specified PT terms
Events			
Guillain-Barre Syndrome	SMQ	Narrow	Specified PT terms

mRNA-1010-P303

Haematopoietic Cytopenias	SMQ	Narrow	Specified PT terms	
Hearing and Vestibular	SMQ	Narrow	Specified PT terms	
Disorders			_	
Hypersensitivity	SMQ	Narrow	Specified PT terms	
Immune-	SMQ	Narrow	Specified PT terms	
mediated/Autoimmune			-	
Disorders				
Ischaemic Heart Disease	SMQ	Narrow	Specified PT terms	
Noninfectious	SMQ	Narrow	Specified PT terms	
Myocarditis/Pericarditis			_	
Peripheral Neuropathy	SMQ	Narrow	Specified PT terms	
Thrombophlebitis	SMQ	Narrow	Specified PT terms	
Vasculitis	SMQ	Narrow	Specified PT terms	
*Based on MedDRA 25.0				
** Narrow + Broad search may also be applied, as needed.				

Table 21 Algorithm Approach for Anaphylactic Reaction

The following criteria will be used to determine anaphylactic reaction:

- A term from Category A
- A term from Category B (Upper Airway/Respiratory) and a term from Category C (Angioedema/Urticaria/Pruritus/Flush) that occurred within 24 hours of each other.
- A term from Category D (Cardiovascular/Hypotension) and at least one of the following:
 - A term from Category B (Upper Airway/Respiratory) that occurred within 24 hours of each other.
 - A term from Category C (Angioedema/Urticaria/Pruritus/Flush) that occurred within 24 hours of each other.

Anaphylactic Reaction				
Category	Scope	PT Search Term		
А	Narrow	Anaphylactic reaction		
А	Narrow	Anaphylactic shock		
А	Narrow	Anaphylactic transfusion reaction		
А	Narrow	Anaphylactoid reaction		
А	Narrow	Anaphylactoid shock		
А	Narrow	Circulatory collapse		
А	Narrow	Dialysis membrane reaction		
А	Narrow	Kounis syndrome		
А	Narrow	Procedural shock		
А	Narrow	Shock		
А	Narrow	Shock symptom		
А	Narrow	Type I hypersensitivity		
В	Broad	Asthma		
В	Broad	Bronchial oedema		

mRNA-1010-P303

Date Issued: 03APR2024

В	Broad	Bronchospasm
В	Broad	Cardio-respiratory distress
В	Broad	Chest discomfort
В	Broad	Choking
В	Broad	Choking sensation
В	Broad	Circumoral oedema
В	Broad	Cough
В	Broad	Cough variant asthma
В	Broad	Cyanosis
В	Broad	Dyspnoea
В	Broad	Hyperventilation
В	Broad	Irregular breathing
В	Broad	Laryngeal dyspnoea
В	Broad	Laryngeal oedema
В	Broad	Laryngospasm
В	Broad	Laryngotracheal oedema
В	Broad	Mouth swelling
В	Broad	Nasal obstruction
В	Broad	Oedema mouth
В	Broad	Oropharyngeal oedema
В	Broad	Oropharyngeal spasm
В	Broad	Oropharyngeal swelling
В	Broad	Pharyngeal oedema
В	Broad	Pharyngeal swelling
B	Broad	Respiratory arrest
B	Broad	Respiratory distress
B	Broad	Respiratory failure
B	Broad	Reversible airways obstruction
B	Broad	Sensation of foreign body
B	Broad	Sneezing
B	Broad	Stridor
B	Broad	Swollen tongue
В	Broad	Tachypnoea
В	Broad	Throat tightness
В	Broad	Tongue oedema
B	Broad	Tracheal obstruction
B	Broad	Tracheal oedema
B	Broad	Upper airway obstruction
В	Broad	Vaccine associated enhanced respiratory disease
В	Broad	Wheezing
С	Broad	Allergic oedema
С	Broad	Angioedema
С	Broad	Circumoral swelling
С	Broad	Ervthema
С	Broad	Eve oedema
C	Broad	Eve pruritus
C	Broad	Eve swelling
C	Broad	Evelid oedema
C	Broad	Face oedema
C	Broad	Flushing
C	Broad	Injection site urticaria
C	Broad	Lin oedema
C	Broad	Lip svelling
	L L L L L L L L L L L L L L L L L L L	

mRNA-1010-P303

Date Issued: 03APR2024

С	Broad	Nodular rash
С	Broad	Ocular hyperaemia
С	Broad	Oedema
С	Broad	Oedema blister
С	Broad	Periorbital oedema
С	Broad	Periorbital swelling
С	Broad	Pruritus
С	Broad	Pruritus allergic
С	Broad	Rash
С	Broad	Rash erythematous
С	Broad	Rash pruritic
С	Broad	Skin swelling
С	Broad	Swelling
С	Broad	Swelling face
С	Broad	Swelling of eyelid
С	Broad	Urticaria
С	Broad	Urticaria papular
D	Broad	Blood pressure decreased
D	Broad	Blood pressure diastolic decreased
D	Broad	Blood pressure systolic decreased
D	Broad	Cardiac arrest
D	Broad	Cardio-respiratory arrest
D	Broad	Cardiovascular insufficiency
D	Broad	Diastolic hypotension
D	Broad	Hypotension
D	Broad	Hypotensive crisis
D	Broad	Post procedural hypotension
